VA BIC Intervention Description: Patients assigned to the VA BIC intervention will receive the VA BIC plus the standard psychiatric hospital discharge care. The VA BIC is an adaptation of the successful WHO BIC intervention and designed to meet the unique needs of Veterans receiving care in the VA medical system (**see VA BIC Manual, Appendix 1**). VA BIC can be delivered by a trained mental health staff member, such as a mental health nurse, social worker, or psychiatrist. The VA BIC targets the needs of patients who are being discharged from a VA inpatient mental health unit after having been admitted because of acute suicide risk. The VA BIC incorporates aspects of motivational interviewing (MI). Since the VA BIC is designed to enhance the standard hospital discharge care that patients receive as part of psychiatric hospitalization, patients assigned to the VA BIC will continue to have access to standard discharge care (described below). There are no restrictions on the types of treatments that patients may pursue after discharge.

- Brief Educational Intervention: Patients receive a one-hour, one-on-one, brief educational intervention on suicide prevention. The session is performed by a VA BIC intervention staff member and takes place on the inpatient mental health unit around the time of discharge. We anticipate that, in most cases, the patients will receive the intervention the day prior to discharge. The education is designed to meet the information needs of Veterans receiving mental health care in the VA and to address patient barriers to follow-up. The education includes a discussion of the patient's safety plan. The sessions are highly interactive, allowing time for questions and providing patients with written materials that they can keep for future reference.

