- Regular Contact: The patients will maintain regular contact with the same VA BIC intervention staff member for a total of six contacts over the course of the three months after psychiatric hospitalization. At each of these contacts, the VA BIC intervention staff member will monitor the patient's symptoms, assess treatment adherence, review the safety plan with the patient, and, if necessary, assist the patient with engaging in care. The contact sessions will be systematic and structured. The contacts are designed to be highly interactive, allowing times for questions and providing patients with written materials that they can keep for future reference. Depending on the patient's preference, the regular contacts will be delivered over the phone (or VA Video Connect) or in-person in a private office on the grounds of the WRJ VAMC. These visits last roughly 15-30 minutes.

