- Patient activation: Patient activation is defined as "an individual's knowledge, skill and confidence for managing their health and health care."⁴⁵⁻⁴⁶ Individuals who demonstrate higher degrees of patient activation have been found to be more likely to engage in health-promoting behaviors and to experience better outcomes.⁴⁷ We will measure activation using the validated Partners in Health (PIH) scale.⁴⁸ The PIH is a 12-item generic instrument that is used to measure patient self-management of chronic conditions.⁴⁸ It includes three domains of self-management including knowledge of condition, partnership in treatment, and coping with the condition. It has good reliability and validity in patients with chronic conditions.⁴⁹⁻⁵⁰ The psychometric properties of the PIH in Veterans have not been studied.
- Continuity of care: There is some evidence that improved continuity of care may lead to better mental health outcomes.⁵¹⁻⁵² However, a single, valid, standardized measure of continuity of care for mental health has not been described in the literature. Work by Greenberg *et al.* in Veterans who were discharged from a VA inpatient mental health unit provides sufficient evidence that three aspects of continuity of care after psychiatric hospitalization (regularity of care, continuity of treatment across organizational boundaries, and intensity of treatment) are associated with improvements in overall mental health.⁸ We will use the three measures of continuity of care as validated by Greenberg *et al.* This includes:
 - a) Continuity of care: Measure of whether a patient discharged from the inpatient MH unit received any MH outpatient treatment in the first month and between 1 – 3 m after discharge.
 - b) Regularity of care: The number of months in the 3 m after the initial assessment in which the patient attended at least 1 MH visit (Range 0 3 m), and
 - c) Intensity of care: Measure of the total number of MH visits between initial entry into the study and the last study assessment).

In addition, we will also evaluate evidence of disruptions of care including no-show and cancelled appointments. We will abstract these measures from the electronic medical record. Since it is possible that some patients may receive portions of their care outside of the VA system, we will also ask patients to self-report on non-VA care.

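### The engagement measures drawn from the medical record do not say whether the six VA BIC contacts count as mental health visits; if they do, intensity of care in particular would partly measure delivery of the intervention

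*Combined protocol and SAP*

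**What the plan says.** Under Outcome Measures, Secondary Outcome (Patient Engagement), the protocol defines three record-based measures:

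- Intensity of care: "Measure of the total number of MH visits between initial entry into the study and the last study assessment".
- Regularity of care: the number of months, from 0 to 3, "in which the patient attended at least 1 MH visit".
- Continuity of care: "Measure of whether a patient discharged from the inpatient MH unit received any MH outpatient treatment in the first month", and again for the period from one to three months.

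On the source it says: "We will abstract these measures from the electronic medical record". Patients also self-report non-VA care. No-shows and cancellations are collected as disruptions of care.

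The VA BIC Intervention Description states: "VA BIC can be delivered by a trained mental health staff member, such as a mental health nurse, social worker, or psychiatrist". Under Regular Contact, intervention patients stay in touch with the same staff member "for a total of six contacts over the course of the three months after psychiatric hospitalization". At each contact "the VA BIC intervention staff member will monitor the patient's symptoms, assess treatment adherence, review the safety plan with the patient". As to mode, "the regular contacts will be delivered over the phone (or VA Video Connect) or in-person in a private office". A one-hour education session precedes these contacts and is given on the inpatient unit around discharge.

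Statistical Analyses, Specific Aim 2, lists regularity, continuity and intensity among the continuous engagement measures, to be compared between arms by ANCOVA at one and three months. The hypothesis for Specific Aim 2 is that VA BIC improves patient engagement.

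**The concern.** The window for the counts and the window for the contacts are the same three months, and only one arm has the contacts. They last roughly 15 to 30 minutes, may be given by a mental health nurse, social worker or psychiatrist, and deal with symptoms, treatment adherence and the safety plan. Elsewhere the protocol itself calls them visits (Specific Aims/Purpose; Therapeutic Risks). An abstractor who finds them in the record and applies the definitions as written has no stated reason to leave them out.

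One stated purpose of the contacts is to help patients engage in care. The informative outcome is therefore care received beyond VA BIC. If the contacts are included, a between-arm difference can appear although attendance at other care is unchanged, and it would be read as support for the engagement part of Aim 2. The programme is meant for dissemination to rural facilities, so such a reading would have practical consequences.

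**Working it through.** **No planned figure to reproduce.** The protocol gives no expected value, SD or power for intensity, regularity or continuity. What follows is illustrative, and the assumptions are marked.

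**Inputs from the documents**
- Six contacts over three months, intervention arm only (Regular Contact; Study Design).
- 25 patients from Ground East, permuted blocks intended to give equal arms (Randomization; Study Population and Recruitment). This is taken as 13 v 12.
- Significance at P < 0.05 (Statistical Analyses). Sidedness is not stated; two-sided is assumed.
- Both arms: two follow-up visits arranged within 30 days, or four on the Suicide Prevention Pathway (Standard Psychiatric Hospital Discharge Care).

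**Assumptions**
- SD of total MH visits: 4, 6, 8 or 10.
- Contacts completed, charted as MH visits and counted, per intervention patient: six or three.
- No true effect on any other care.
- A two-sample t-test stands in for the planned ANCOVA.

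**Intensity.** If k contacts are counted, the built-in mean difference is k visits. The noncentrality parameter is k / (SD × √(1/13 + 1/12)) = k / (0.4003 × SD), with 23 degrees of freedom and critical value 2.069. For k = 6 and SD = 6 this is 6 / (0.4003 × 6) = 2.50, and the chance of P < 0.05 is 0.667.

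| Assumed SD | Six counted | Three counted |
|---|---|---|
| 4 | 0.948 | 0.435 |
| 6 | 0.667 | 0.224 |
| 8 | 0.435 | 0.146 |
| 10 | 0.301 | 0.111 |

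With no contacts counted the difference is zero and the chance is the nominal 0.05.

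**Regularity and continuity.** Let p be the chance of other MH care in a period, and assume a 90% chance of at least one VA BIC contact in it. The intervention arm's chance becomes 1 − (1 − p) × 0.1. For p = 60%, 80% and 95% this is 96%, 98% and 99.5%. Mean regularity, three times the monthly chance, goes from 1.80 to 2.88, 2.40 to 2.94, and 2.85 to 2.99 months. At 12 per arm the chance of a false significant result is about 98%, 70% and 7% for regularity (simulated t-test, 5,000 runs) and 57%, 28% and 10% for continuity (two-proportion approximation, rough at this size). The artefact therefore fades as attendance at other care rises. It is small only when that attendance is high.

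**The case against.** The strongest objection is that the bias needs a fact the protocol does not supply: that VA BIC contacts are charted as MH visits. The intervention description says only that mental health staff can deliver VA BIC. Resources Available lists the interventionist among the research staff. Protected Health Information describes study data as going into an electronic data-capture system and VA utilization as coming from the medical record, which suggests separate streams without establishing them. A counting rule could also sit in the VA BIC Manual, the Assessment Manual or the cited study whose measures are adopted, none of which is available here. All of this stands, and it makes the point conditional. It does not remove it, because the result would still depend on a charting and coding choice that the plan leaves open.

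A reader might go further and infer several things that the documents do not support:

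- *The intervention arm wins all three measures by construction.* This needs the charting premise above. In addition, regularity stops at three months, continuity is any or none, and standard care already arranges two visits within 30 days in both arms.
- *Seven sessions are added.* The education session takes place on the inpatient unit, so it cannot enter a measure of outpatient treatment. It reaches intensity only if inpatient sessions count as MH visits.
- *The effect is near certain in a pooled comparison of 50 v 50.* The six-contact schedule is specified for Ground East. Versions for the other settings are still to be developed, and the whole-sample analysis is described for Aim 1, not Aim 2.
- *Aim 2 as a whole would be answered yes.* The PIH, BHS and INQ-15 are analysed separately, and the protocol itself warns that attendance alone may not reflect engagement.

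Finally, not every effect of the gap favours VA BIC. Missed VA BIC contacts, if counted as disruptions of care, would work against it.

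**Conclusion.** The point holds as a conditional one, centred on intensity of care. The definitions neither include nor exclude the six post-discharge contacts. If those contacts are charted as MH visits, literal application credits the intervention's own delivery as engagement.

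In the Ground East trial the chance of a false significant intensity result would then be about 30% to 95% with six contacts counted and 11% to 43% with three, over assumed SDs of 10 down to 4 visits. These ranges rest on assumed SDs, assumed numbers of counted contacts and a t-test; the direction of the shift does not depend on the SD. Regularity and continuity are lesser risks where attendance at other care is high. The two visits arranged in the first 30 days support that for the first month but do not speak to the later ones.

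The primary BSS outcome and the PIH, BHS and INQ-15 are not affected. The change should be made before abstraction begins, and before later amendments carry the definitions to other settings.

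**What to change.** In the outcome definitions, state that MH visits and MH outpatient treatment, for intensity, regularity and continuity, exclude VA BIC education and contact sessions and study assessment visits. Apply the same exclusion to no-shows and cancellations in disruptions of care, so that missed VA BIC contacts are not scored there. Flag these sessions at abstraction in the same way for both arms, and report VA BIC contacts separately as intervention adherence. If one of the appendices already contains such a rule, a cross-reference is enough.

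The cost is a sentence or two in the outcome definitions and one extra flag on the abstraction form, with no new data. The engagement result may be less favourable to VA BIC, but it would describe care beyond the intervention.

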secondary	Connectedness	INQ-15	0.89 – 0.91	15 items	5	Х	Х	X					
outcomes	Suicide Attempts	CSSR-S	N/A	7 items	5-10	Х	Χ	Х					
throughout the study. Copies of	Estimated time (in m	45	45	45									
the assessment tools are available in the Assessment Manual (App 2).	BHS = Beck Hopelessness Scale; BSS = Beck Scale for Suicidal Ideation; CSSR- S = Columbia Suicide Severity Rating Scale; INQ-15 = Interpersonal Needs Questionnaire-15; M = months; N/A = Not applicable; PIH = Partners in Health; *Time is described in minutes												

Baseline Characteristics: We will collect socio-demographic data from the electronic medical record such as age, sex, marital status and service history (e.g., branch, era, combat exposure). With regards to diagnostic information, we will administer the MINI International Neuropsychiatric Interview (MINI) at study entry. The MINI is a short, structured diagnostic interview that takes about 15 minutes to administer.³⁵ It has been validated against the Structured Clinical Interview for Diagnostic and Statistical Manual of Mental Disorders (DSM). We will inquire about any history of suicide attempts using the validated Columbia Suicide Severity Rating-Scale (C-SSRS).³⁶ The C-SSRS includes a seven-item subscale that assesses for actual and interrupted suicide attempts.

Primary Outcome (Suicidal Ideation): The primary outcome will be assessed using the Beck Scale for Suicidal Ideation (BSS) (Specific Aim 1).^{2,37} Patients will be asked about their current suicidal ideation (i.e., past week) at baseline and at follow-up assessments. The BSS is a self-reported questionnaire that assesses severity of suicidal ideation. The BSS measures attitudes, behaviors, and plans to die by suicide. Each item on the BSS is scored on a scale from 0 to 2 and the first 19 of the 21 items are used to calculate a total score ranging from 0 - 38. The BSS has high reliability and is a valid measure of suicidal ideation. There is also evidence that the BSS is measurement invariant across time. ³⁸ The BSS is widely used in clinical trials, is

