 - A) Clean and analyze data from trial of VA BIC for patients being discharged from an inpatient mental health unit.
 - B) Finalize VA BIC manual for patients being discharged from an inpatient mental health unit based on results.
 - C)Enroll 25 veterans in a randomized trial of VA BIC for patients being discharged from an inpatient medical/surgical unit after receiving psychiatric consultation.
 - D) Pilot an adapted version of VA BIC in 3 veterans being discharged from a residential substance treatment facility.
 - E)Enroll 13 veterans in a randomized trial of VA BIC for patients being discharged from a residential substance treatment facility.
 - F)Develop an adapted version of VA BIC for patients being discharged from an emergency room after presenting with a mental health concern.
- 3) Year 3: We will complete seven deliverables during the third year: (We will submit a study amendment prior to conducting the work described below)
 - A) Clean and analyze data from trial of VA BIC for patients being discharged from an inpatient medical/surgical unit after receiving psychiatric consultation.
 - B) Finalize VA BIC manual for patients being discharged from an inpatient medical/surgical unit after receiving psychiatric consultation based on results.
 - C)Enroll 12 veterans in a randomized trial of VA BIC for patients being discharged from a residential substance treatment facility.
 - D) Clean and analyze data from trial of VA BIC for patients being discharged from a residential substance treatment facility.
 - E) Finalize VA BIC manual for patients being discharged from a residential substance treatment facility.
 - F) Pilot an adapted version of VA BIC in 3 veterans following discharge from an emergency room after presenting with a mental health concern.
 - G)Enroll 25 veterans in a randomized trial of VA BIC for patients being discharged from an emergency room after presenting with a mental health concern.
- 4) Year 4: We will complete ten deliverables during the fourth year: (*We will submit a study amendment prior to conducting the work described below*)
 - A) Clean and analyze data from trial of VA BIC for patients being discharged from an emergency room after presenting with a mental health concern.
 - B) Finalize VA BIC manual for patients being discharged from an emergency room after presenting with a mental health concern.
 - C)Integrate VA BIC trial data across high-risk care transition scenarios and analyze results.

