Statistical Analyses: To maintain blinding, the statistician who is otherwise not directly involved in the study will conduct the analysis based on the intention-to-treat principle. Below, we have outlined the specific analysis plan for assessing each of the primary and secondary aims of interest of this study. We will assess for statistically significant differences in baseline study characteristics such as age, sex, race, and mental health diagnosis, between study arms using *t*-tests for continuous measures and chi-squared tests for dichotomous variables. We will report these results using 95% confidence intervals (CI) and *P*-values. We will define statistical significance as a *P*-value < 0.05. If we identify any variables for which there are significant differences across study arms, we will control for these confounders in the analysis of the aims.

Specific Aim 1: We will generate descriptive summary statistics (e.g., means and standard errors, medians) and graphical displays for the BSS total scores at baseline and at each of the follow-up assessments. For each of the four acute care settings included in our study, we will perform simple statistical tests. First, we will use a repeated measures analysis of variance (ANOVA) test to assess for changes in continuous variables in the first three months after discharge. Second, if the repeated measures ANOVA suggested a significant difference in means across time, we will perform a post-hoc, pair-wise comparison of means at baseline and one- and three-month follow-up using a two-sample t-test.

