We will perform a more complex analysis for the entire study sample at the end of the four years because we will have adequate power to do so. The following outlines are specific approach: Based on available evidence, we hypothesize that the VA BIC program plus standard hospital discharge care will lead to a significant reduction in suicidal ideation after discharge from an acute care setting. We believe that the effect of VA BIC on suicidal ideation will be the greatest at the three-month follow-up because the greatest intensity of follow-up care provided through VA BIC occurs within the first three months after discharge. We will generate descriptive summary statistics (e.g., means and standard errors, medians) and graphical displays for the BSS total scores at baseline and at each of the follow-up assessments. Because BSS scores are typically over dispersed, it is not appropriate to use standard parametric statistics. Therefore, we will treat the BSS scores as count data and use negative binomial regression. Specifically, we will use a generalized linear mixed model. We will consider allocation of study arm (categorical measure) and time (continuous measure) as fixed effects. Random effect will be used to account for correlation that arises from repeated measures of the same individual. We will assume a linear effect and model changes in suicidal ideation over time. We will calculate 95% CI and P-values and will define a *P*-value of < 0.05 to be statistically significant. We will use the maximum likelihood ratio to account for any missing data.

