Specific Aim 2: First, we will perform an analysis to demonstrate whether there are greater improvements in patient engagement, hopelessness, and perceived connectedness over time in patients assigned to the VA BIC intervention versus control condition at one, three months after discharge. For continuous variables measuring patient engagement (PIH, Hopelessness, Regularity of Care, Continuity of Care across Organizational Boundaries, and Intensity of Care) and perceived connectedness (INQ-15), we will generate descriptive summary statistics (e.g., means and standard errors, medians) and graphical displays for each measure at baseline and at each of the follow-up assessments. Second, using analysis of covariance (ANCOVA), we will calculate mean differences in scores for each of our continuous measures at the one-and three-month follow-up, as well as the associated 95% confidence intervals and *P*-values. For the categorical measure of disruptions in care, we will use chi-squared tests to compare the proportion of patients experiencing disruptions in care between the two study arms at one- month and three-months after discharge.

Specific Aim 3: While suicide deaths and suicide attempts are important clinical endpoints, this single-site trial will not be powered to detect a statistically significant effect between study arms. Furthermore, because we assume that few events will be observed in either arm, we plan to summarize our findings by providing basic descriptive statistics regarding the number of events in each arm at one-and three-month follow-ups.

Randomization: Prior to the start of study enrollment, the statistician will independently prepare allocation cards using a permutated block schedule. The advantage of this approach is that it ensures that an equal number of participants are assigned to each arm.⁵⁶ The statistician will the put these cards into sealed, opaque, numbered envelopes. The box of envelopes will be stored in a locked cabinet in the study coordinator's locked office.

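### Covariates for Aims 1 and 2 are chosen by baseline significance tests between randomised arms, and baseline BSS is not a named covariate

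*Combined protocol and SAP*

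**What the plan says.** Under Statistical Considerations, the Statistical Analyses paragraph plans t-tests and chi-squared tests of "baseline study characteristics such as age, sex, race, and mental health diagnosis, between study arms", with significance at P < 0.05. For "any variables for which there are significant differences across study arms, we will control for these confounders in the analysis of the aims". Sidedness is not stated. Nor is it stated whether the tests are run within each care setting or once on the pooled sample.

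For Aim 1 there are two layers. Within each setting there is a repeated measures ANOVA and, if that is significant across time, a "pair-wise comparison of means at baseline and one- and three-month follow-up using a two-sample t-test". For the whole sample there is a negative binomial mixed model: "We will consider allocation of study arm (categorical measure) and time (continuous measure) as fixed effects", with a random effect for the patient, and "We will assume a linear effect and model changes in suicidal ideation over time". Neither layer names a baseline covariate, and the pooled model does not name care setting.

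For Aim 2, "using analysis of covariance (ANCOVA), we will calculate mean differences in scores for each of our continuous measures" at one and three months; the covariate is not named. Aim 3 is descriptive.

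Baseline BSS is available. The Primary Outcome paragraph says: "Patients will be asked about their current suicidal ideation (i.e., past week) at baseline and at follow-up assessments". The settings are analysed one at a time; the Year 2 deliverables include: "Clean and analyze data from trial of VA BIC for patients being discharged from an inpatient mental health unit".

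**The concern.** When allocation is random, a significant baseline difference is a chance event. It says nothing about whether the variable predicts outcome, and predicting outcome is what makes adjustment worthwhile. Baseline BSS is the obvious candidate to predict later BSS, yet under this rule it would be adjusted for only after an unlucky draw.

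The covariate set is also unknown until the baseline data have been tested. If the tests are run per setting, chance decides which of the four settings are adjusted and for what. The Specific Aims/Purpose section wants the per-setting results to show facilities which populations benefit most. With 25 patients per setting, precision is scarce.

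**Working it through.** **Inputs.** From the Sample Size paragraph: 100 patients, 25 per setting. From the Randomization paragraph: equal arms, so 12 v 13 per setting and 50 v 50 pooled. From Statistical Analyses: P < 0.05, taken as two-sided. The documents give no SD, baseline-to-follow-up correlation r, dropout rate or numeric power, so there is no stated figure to reproduce. Assumed: Gaussian data, no dropout, r = 0.3, 0.5 and 0.7, and a month-3 effect of 0.566 SD. That effect is the one an unadjusted t-test on 50 v 50 detects with 80% power.

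**When the rule fires.** The difference needed is t × √(1/n₁ + 1/n₂):
- 12 v 13: 2.069 × √(1/12 + 1/13) = 2.069 × 0.400 = 0.83 SD.
- 50 v 50: 1.984 × √(2/50) = 1.984 × 0.200 = 0.40 SD.

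A continuous baseline variable crosses that line in 5% of trials, however prognostic it is. At 12 v 13, an imbalance of 0.5 SD or more has probability 2 × [1 − Φ(0.5/0.400)] = 0.212, and at most 0.05/0.212 = 24% of such imbalances are flagged.

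**How data-dependent the covariate set is.** Four independent tests at exactly 5% give at least one flag with probability 1 − 0.95⁴ = 18.5%. At 12 v 13, with one continuous and three binary variables at 10% to 30% prevalence, this is 10% to 19% with uncorrected chi-squared tests and 5% to 9.5% with continuity correction. If the tests are run per setting, the chance that at least one of the four settings is adjusted, 1 − (1 − q)⁴, is about 35% to 57% uncorrected and 19% to 33% corrected.

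**Cost of the rule per setting.** This part needs two readings that the text leaves open: the t-tests compare arms at month 3, and baseline BSS is among the variables tested.
- Unadjusted: SE 0.400, non-centrality 0.566/0.400 = 1.41, power 27%.
- Always adjusted: SE is 0.400 × √(1 − r²) = 0.382, 0.347 and 0.286, before a small allowance for estimating the regression slope.
- Under the rule, about 95% of trials use the unadjusted test. Simulation gives the following:

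| r | Rule, power | Always adjusted, power | Rule, rejection under the null |
|---|---|---|---|
| 0.3 | 27% | 28% | 4.9% |
| 0.5 | 27% | 33% | 4.4% |
| 0.7 | 27% | 46% | 3.6% |

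The mean estimate under the rule was 0.56 to 0.57, against a true 0.566.

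**The pooled model, a separate matter.** Read it as an arm-by-time slope over months 0, 1 and 3 with a free baseline difference. The mean time is 4/3, and the sum of squares is 16/9 + 1/9 + 25/9 = 14/3. Under equal correlation between visits, the month-3 effect (3 × slope) has per-patient variance 9(1 − r)/(14/3) = (27/14)(1 − r). A month-3 comparison adjusted for baseline has 1 − r².
- Slope: 1.35, 0.964, 0.579.
- Adjusted: 0.91, 0.75, 0.51.
- Ratio, (27/14)/(1 + r): 1.48, 1.29, 1.13.

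This is a linear-model illustration, not the planned negative binomial model.

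**The case against.** The strongest reply is that the trigger and the pooled model are different things. The 1.48, 1.29 and 1.13 ratios come from how the pooled model handles baseline, not from the P < 0.05 rule; deleting the rule alone would recover none of that loss. This stands, and the two are kept apart here. The ratios also assume an arm-by-time reading. Taken literally, with arm and time and no interaction, the model is a different one and they do not apply.

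The per-setting powers rest on an ambiguous sentence. The t-tests follow an ANOVA difference across time and could be read as comparing time points rather than arms. The preceding ANOVA step was not simulated, and at r = 0.3 the loss is one point. This also stands: the powers are conditional. The selection rule itself is not ambiguous.

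Stronger readings are tempting, but the documents do not support them:
- That the rule biases the estimate or inflates type I error. It looks at baseline data only; the simulated rejection rate under the null is below 5%.
- That every aim is affected. Aim 3 is descriptive and has no test to adjust.
- That no covariate is planned at all. ANCOVA in Aim 2 implies one, most naturally the baseline score; what is missing is its name.
- That Aim 1 ignores baseline BSS. It is measured at months 0, 1 and 3 and enters as a repeated response.

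**Conclusion.** The point holds for Aims 1 and 2 as one of efficiency and pre-specification. Chance baseline differences decide the covariates, from an open list that does not name baseline BSS. If tested, that score would be adjusted for in about 5% of trials.

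The loss per setting runs from 1 to 19 percentage points of power (27% v 28% to 46%) across r = 0.3 to 0.7, given the two readings and the assumed effect and distribution. The size therefore turns on a correlation the documents do not give. The pooled model carries a separate loss that is largest at low r. Neither threatens validity, but both are avoidable with data the trial already collects, so the text should be changed.

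**What to change.** Delete the baseline significance tests and the adjustment trigger, and report baseline characteristics by arm descriptively.

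For Aim 1, per setting and pooled, pre-specify baseline BSS in one of two ways, not both:
- as a covariate, with only the one- and three-month scores as outcomes; or
- as a response, with its baseline mean constrained equal across arms.

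Per setting, this replaces the two-sample t-test, which cannot take a covariate, with ANCOVA or an equivalent model.

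Two minor additions: include care setting as a fixed effect in the pooled model, and name the baseline score as the ANCOVA covariate for the Partners in Health scale, the Beck Hopelessness Scale and the INQ-15. The gain from setting is small. If setting carries 10% to 30% of the variance (assumed), omitting it multiplies the variance by 1.04 to 1.16 once baseline BSS is adjusted for, and by 1.00 for an arm-by-time effect. Any further covariates should be fixed before unblinding and used only in sensitivity analyses.

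The cost is revised analysis text, including a changed per-setting method, and about four degrees of freedom (one for baseline BSS, three for setting in the pooled model). No new data, visits or patients are needed. The protocol already plans amendments before the Year 2 to Year 4 work, so the per-setting text can be settled before the first setting is analysed in Year 2, and the pooled model before Year 4.
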